8.6 Adverse Events Monitoring

Refer to the Data Safety Monitoring Plan, located in Appendix 2.

8.7 Pregnancy and Exposure during Breastfeeding

Although pregnancy and infant exposure during breastfeeding are not considered AEs, any pregnancy or infant exposure during breastfeeding in a participant (spontaneously reported to the investigator or their designee) that occurs during the study are reportable to Merck.

All reported pregnancies must be followed to the completion/termination of the pregnancy. Pregnancy outcomes of spontaneous abortion, missed abortion, benign hydatidiform mole, blighted ovum, fetal death, intrauterine death, miscarriage, and stillbirth must be reported as serious events (Important Medical Events). If the pregnancy continues to term, the outcome (health of infant) must also be reported.

9 Statistical Considerations and Evaluation of Results

This study will utilize a Simon's two-stage design with 15 participants enrolled in stage I and 10 additional participants enrolled in stage II assuming that at least 2 or more participants achieve a treatment response after 4 cycles of therapy during stage I of the study. The primary endpoint will be overall response rate (partial response [PR] or better) after 4 cycles of therapy. A Bayesian toxicity monitoring design will be incorporated for ongoing safety analysis during the trial to pause enrollment if at any time the rate of grade 3 or higher non-hematologic adverse events exceeds 30%.

9.1 Sample Size Considerations

9.1.1 Sample Size and Power Estimate

The primary endpoint is the overall response rate (ORR), defined as the proportion of patients achieving a partial response (PR) or better after 4 cycles of pembrolizumab therapy. Simon's minimax two-stage design will be used to test the null hypothesis that the true ORR is 10% against a one-sided alternative that the true ORR is higher than 30%. The two-stage minimax design described below will have an 80% power to reject the null hypothesis that ORR is 10% at one-sided Type I error rate of 5%, assuming that the ORR is 30%.

Stage 1: 15 participants will be accrued. The trial will be terminated at Stage 1 if 0 or 1 response is observed; otherwise, it will continue to Stage 2. Response rate for Stage I will be determined based on patients who have completed at least 4 cycles of therapy or have progressive disease after at least one cycle of therapy; participants who withdraw or drop out due to toxicities before meeting these endpoints will not be used in the analysis of response and will be replaced.

Stage 2: 10 more patients will be accrued (for a total of 25 patients). We will reject the null hypothesis if 6 or more responses are observed in 25 patients.

Early stopping probability: Under this design, if the true response rate is 10%, the probability of stopping the trial early will be 55%.

We plan to enroll 25-27 participants to allow for the possibility of 10% participant dropout before receiving pembrolizumab therapy or during the response evaluation period.

9.1.2 Accrual Estimates

We anticipate enrolling approximately 12 – 15 patients a year. As an active clinical trial site and a center that offers commercial anti-BCMA CAR-T, we anticipate 30 to 50 patients to receive anti-BCMA CAR-T on a yearly basis; the majority of these patients will ultimately have disease progression, allowing for enrollment in this clinical trial.

9.2 Interim Analyses and Stopping Rules

The clinical trial will be stopped for futility if after the first stage of Simon two-stage trial (after fifteen evaluable participants enrolled), there are only zero or one participant who responds with PR or better according to IMWG.

There will also be monitoring for adverse events, specifically for non-hematologic grade 3 or higher adverse events. If at any point it is expected that the rate of grade 3 or higher non-hematologic AE exceeds 30%, enrollment will be paused for safety review by the HDFCCC data and safety monitoring committee, study sponsor, and study PI. If after this safety review is conducted and the study is deemed unsafe to continue, the study will be stopped.

Previous data suggested a severe grade 3-4 AE rate of around 15-20% in pembrolizumab monotherapy trials across various cancers^{17,37-40}. These events would be expected to be 15-20% in this study irrespective of cause. Hence, we will render the study treatment tolerable in this population if the observed severe adverse event rate is <30%. We will report the toxicity and advise the providers regarding excessive toxicity and pause enrollment for a safety review if at any point it is expected that the rate of grade 3 or higher non-hematologic AE exceeds 30%. Moreover, the study will be stopped and the FDA will be informed if at any point it is expected that the rate of Grade 4 or higher adverse events (including Grade 4 CRS and treatment-related immunologic AEs) or any treatment-related death exceeds 30%. In this case, the FDA must approve the study's resumption prior to re-initiation of enrollment and study treatment.

Specifically, we will apply a Bayesian toxicity monitoring rule with Beta (0.6, 3.4) as the prior distribution. This means that our prior guess of the proportion of toxicity is 15%, and there is 90% chance that the rate of toxicity is 0.2%-48.9%. We will suspend enrollment if the posterior probability that the toxicity rate exceeds the threshold (30%) is 70% or higher and stop the study if the rate of Grade 4 or higher adverse events (including Grade 4 CRS and treatment-related immunologic AEs) or any treatment-related death meets these parameters. The monitoring will start from the first patient, and the decision rule for a safety pause/stop is as follows:

Pause if at any time:

# toxicity and death	Out of # patients
2	2
3	3-5
4	6-8
5	9-11
6	12-14
7	15-17
8	18-20
9	21-23
10	24-25

Study enrollment will also be paused for safety review if any participants encounter:

- Treatment-related death
- Grade 4 toxicity (excluding clinically insignificant/temporary laboratory abnormalities)
- Grade 4 CRS or Grade 3 CRS that does not resolve to Grade ≤ 1 or baseline within 48 hours
- Grade 4 ICANS or Grade 3 ICANS that does not resolve to Grade ≤ 1 or baseline within 48 hours

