Given that PD-1 therapies after CAR-T represent a relatively novel treatment paradigm, we will report rates of adverse events as defined by NCI CTCAE V5.0 and ASTCT (for CRS and ICANS). Previous data with pembrolizumab across various cancers have suggested a severe AE rate (Grade 3 or higher) of 15 – 20%^{17,37-40}, and thus we anticipate a similar frequency in our study irrespective of cause. Given that we hypothesize that pembrolizumab may be able to reactivate quiescent CAR-T cells, there is potential for additional toxicity including CRS and ICANS, and thus a reasonable definition of safety would be having less than 30% of all treated participants incurring a Grade 3 or higher non-hematologic adverse event.

Secondary Objective (2): To evaluate the depth of response for patients treated with pembrolizumab who had previously relapsed after or were refractory to anti-BCMA CAR-T therapies.

Secondary Endpoint (2): Rates of stringent complete response (sCR), complete response (CR), very good partial response (VGPR), partial response (PR), stable disease (SD), and progressive disease (PD) at any time during pembrolizumab therapy

Depth of myeloma response has been correlated with progression-free survival³⁵. Thus, we will plan to evaluate depth of response based on the percentage of patients that achieve a complete response (CR), very good partial response (VGPR), partial response (PR), stable disease (SD), or progressive disease (PD) at any time during pembrolizumab therapy.

Secondary Objective (3): To determine time-to-event outcomes, including time-to-next treatment (TNT), progression-free survival (PFS), and overall survival (OS) after initiation of pembrolizumab therapy

Secondary Endpoint (3): TNT, PFS, OS

We will explore time-to-event outcomes with Kaplan-Meier method after initiation of pembrolizumab. These results can potentially be compared to historical controls.

Exploratory Objective: To explore the immune profile after pembrolizumab treatment, including changes in absolute lymphocyte count (ALC) and lymphocyte subsets by flow-cytometry

Exploratory Endpoint: ALC, absolute CD3 T-cell count, absolute CD4 T-cell count, absolute CD8 T-cell count

We will assess whether participants have changes in their immune profile, specifically in their T-cell numbers and composition, after administration of pembrolizumab and will assess whether these changes correlate to clinical response. These analyses will be predominately descriptive and exploratory.

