9.3.2 Secondary Analysis (or Analysis of Secondary Endpoints)

Continuous data will be summarized using descriptive statistics such as means, medians, standard deviations, and ranges. Categorical data will be summarized using frequency counts and percentages. Graphical summaries of selected endpoints may also be presented.

Secondary Objective and Endpoints #1 - Safety and Tolerability Analysis: The safety population will consist of all participants who receive any amount of study treatment. Safety will be assessed by evaluation of AEs. The safety analyses will be performed using the safety population. Specific AEs will be counted once for each participant for calculating rates but will be presented in total in participant listings.

Secondary Objective and Endpoints #2 -Depth of Response

Point estimate and exact binomial confidence interval will be reported for the proportion of patients achieving PD (progressive disease), SD (stable disease), PR (partial response), VGPR (very good partial response), CR (complete response), and sCR (stringent complete response) for best-achieved response at any time during pembrolizumab therapy.

Secondary Objective and Endpoints #3 -Time to Event Outcomes

For overall survival (OS), participants who remain alive at the end of study follow-up will be censored at the time when they are known to be alive. For progression-free survival (PFS), participants without progression or death will be censored at the time of the last evaluable disease assessment, while participants without a disease assessment will be censored at the date of first study treatment received. OS and PFS will be summarized using the Kaplan-Meier (KM) method. The 12-months event-free probabilities, 25th percentile, median, and 75th percentile, along with their corresponding 95% confidence intervals, will be reported. Median duration of response among the responders will be reported along with 95% confidence intervals. Competing risks analysis will be performed for analyzing time to next treatment (TNT), with death as a competing event. For patients who are alive and do not receive the next line of therapy, TNT will be censored at the last study contact. Cumulative incidence function, along with 95% confidence intervals, will be reported for TNT.

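### Treatment is called tolerable on an observed severe AE rate below 30% alone, with no interval or posterior probability attached to the verdict

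*Combined protocol and SAP*

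**What the plan says.** Section 9.2 ties the safety conclusion to the observed rate: "Hence, we will render the study treatment tolerable in this population if the observed severe adverse event rate is <30" percent. The sentence before it gives the expectation: "These events would be expected to be 15-20% in this study irrespective of cause". Section 1.4 sets the same limit and names the event: "a reasonable definition of safety would be having less than 30% of all treated participants incurring a Grade 3 or higher non-hematologic adverse event".

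Neither section attaches a confidence bound, a posterior probability or an error rate to that conclusion. Section 9.3.2 says "The safety analyses will be performed using the safety population", meaning everyone who received any study treatment. It plans counts and percentages for categorical data and specifies exact binomial intervals only for depth of response. For efficacy the error is specified, in Section 9.1.1: "at one-sided Type I error rate of 5%, assuming that the ORR is 30" percent.

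Section 9.2 also has a Bayesian monitoring rule with a Beta(0.6, 3.4) prior. Enrollment is paused for review when the posterior probability that the rate exceeds 30% is 70% or more. That rule governs conduct during the trial. It does not define or qualify the final verdict.

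**The concern.** The 30% figure is the boundary of what the protocol regards as safe, and the verdict depends only on which side of it the observed proportion falls. With about 25 patients, an observed rate just under 30% is compatible with true rates well above it, and the planned output would not show this. A reader of the report would see the word *tolerable* and a percentage. The protocol itself raises the possibility of added toxicity from CAR-T reactivation (Section 1.4), so the reader needs to know which rates the data leave open. At stake is the wording and completeness of the trial's first secondary conclusion.

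**Working it through.** **Inputs**

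- Limit: observed rate <30% (Sections 9.2 and 1.4).
- Expected rate: 15-20% (Section 9.2).
- Prior: Beta(0.6, 3.4); pause when P(rate >30%) ≥ 0.70 (Section 9.2).
- First-stage size and futility rule (Section 9.1.1): "15 participants will be accrued. The trial will be terminated at Stage 1 if 0 or 1 response is observed; otherwise, it will continue to".
- Full size: "10 more patients will be accrued (for a total of 25 patients). We will reject the null hypothesis if 6 or more responses are observed".
- Enrolment: "We plan to enroll 25-27 participants to allow for the possibility of 10% participant dropout".
- Assumption: each treated participant independently has or does not have a Grade 3 or higher non-hematologic AE, with a common probability p.

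**The plan's own figures reproduce**

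- Prior mean: 0.6/(0.6+3.4) = 0.15. The 5th and 95th percentiles are 0.2% and 48.9%, as stated.
- Pause table: the smallest x with P(p > 0.30) ≥ 0.70 under Beta(0.6+x, 3.4+n−x) matches every printed row. At n=25, for example, 10 events give 0.76 and 9 give 0.62.
- Simon design: P(0 or 1 of 15 at ORR 10%) = 0.549, against the stated 55%. Type I error is 0.033 and power at ORR 30% is 0.802.

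The documents state no operating characteristic for the <30% verdict, so there is none to reproduce.

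**Chance of the verdict**

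The largest passing count k is the largest integer with k/n < 0.30. For n=25, 7/25 = 28% passes and 8/25 = 32% does not. P(verdict) = P(X ≤ k), X ~ Binomial(n, p).

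| n | k | p=15% | p=20% | p=30% | p=35% | p=40% |
|---|---|---|---|---|---|---|
| 25 | 7 | 0.97 | 0.89 | 0.51 | 0.31 | 0.15 |
| 26 | 7 | 0.97 | 0.87 | 0.46 | 0.26 | 0.12 |
| 27 | 8 | 0.99 | 0.93 | 0.58 | 0.36 | 0.18 |
| 15 | 4 | 0.94 | 0.84 | 0.52 | 0.35 | 0.22 |

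**Allowing for the pause table**

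Treat every pause as a permanent stop. Carry the distribution of events forward one patient at a time, remove the probability at or above the printed boundary, and sum what is left at 7 or fewer of 25. This gives 0.44 at p=30%, 0.26 at 35% and 0.13 at 40%. It is a limiting case, since Section 9.2 makes a pause a review that may let the trial continue.

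**What a result at the edge of the rule shows**

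- 7/25: exact (Clopper-Pearson) 95% CI 12% to 49%. The posterior is Beta(0.6+7, 3.4+18) = Beta(7.6, 21.4), so P(rate <30%) = 0.70.
- 4/15: exact 95% CI 8% to 55%; posterior P(rate <30%) = 0.74.

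**The case against.** The strongest reply is that about one half at the limit is a property of any cut on an observed proportion placed at that limit. That is true. A reader might go on to infer that the verdict carries no information, and the figures do not support that: at n=25 the rule passes 97% of the time at a true 15% and 15% of the time at a true 40%. A reader might also say the protocol itself calls a 30% rate unacceptable. It acts when the rate exceeds 30% and calls less than 30% safe, so exactly 30% is the boundary.

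Second, participants are protected by other means: the Bayesian table from the first patient, the stop for Grade 4 or higher events or treatment-related death with FDA approval needed to resume, the single-event pauses, and committee review. This stands. The table alone pauses with probability 0.43 by n=25 at a true 30%. The single-event triggers could lower the figures above further, but the documents give no rates from which to say by how much. None of these rules changes what the final report may say after 7/25.

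Third, safety is secondary, and no section makes the verdict a go/no-go criterion; Section 1.4 links further evaluation to response rate alone. So it should not be inferred that a false verdict would carry a failed drug forward. This applies especially at n=15, which arises mainly from futility stops (probability 0.55 at ORR 10%, 0.035 at ORR 30%), where there is no positive response result to support.

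**Conclusion.** The point holds as a reporting defect in a prespecified secondary conclusion. The verdict rests on a point estimate. It is returned with probability 0.46 to 0.58 when the true rate is 30% and 0.26 to 0.36 when it is 35%, over 25 to 27 treated patients. It would cover 7/25, where rates up to 49% are not excluded. The primary efficacy test is unaffected.

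The figures assume independent events with a common rate and a safety denominator of 25 to 27. Treated participants who are replaced for efficacy stay in the safety set, so the actual denominator may differ. Section 9.2 speaks of the severe AE rate just after citing Grade 3-4 data, while Section 1.4 and the monitoring rule specify Grade 3 or higher non-hematologic events. I have used the latter; the arithmetic is the same for either.

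The documents do not support going further and requiring a particular confidence or posterior threshold before the word *tolerable* may be used. That is a trade-off for the sponsor.

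**What to change.** In Sections 9.2 and 9.3.2, report the Grade 3 or higher non-hematologic AE rate in all treated participants, using the actual safety denominator, with an exact 95% CI and the posterior P(rate <30%) under the existing Beta(0.6, 3.4) prior. Replace the unqualified verdict with wording of the form *observed rate below 30%, upper bound X%*, and say explicitly when a rate of 30% or more is not excluded.

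This needs a wording change and one extra line of output, with no patients or procedures. The downside is a less favourable safety statement. At n=25 the two-sided 95% upper limit falls below 30% only with 2 or fewer events (26.0% at 2/25, 31.2% at 3/25). At a true 15%, P(X ≤ 2) is 0.25, so even a drug performing as expected would carry the not-excluded statement about three times in four.

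If the sponsor wants to keep the word *tolerable* with a posterior cut, its operating characteristics should be stated at both sample sizes:

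| Posterior cut | Passing count | At true 15% | At true 30% |
|---|---|---|---|
| Current rule | ≤4/15; ≤7/25 | 0.94; 0.97 | 0.52; 0.51 |
| 80% | ≤3/15; ≤6/25 | 0.82; 0.93 | 0.30; 0.34 |
| 90% | ≤2/15; ≤5/25 | 0.60; 0.84 | 0.13; 0.19 |

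The 90% cut is costly at n=15, and its largest passing results still have 95% upper limits of about 40% (2/15) and 41% (5/25). The interval should therefore be printed whichever cut, if any, is chosen.

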9.3 Analysis Plans

9.3.1 Primary Analysis (or Analysis of Primary Endpoints)

Participants that complete at least 4 cycles of therapy or have progressive disease after at least one cycle of therapy will be included in the analysis.

To account for the adaptive nature of Simon's two-stage design, final analyses for the primary endpoint will calculate the uniformly minimum variance unbiased estimator (UMVUE), p-value, and 95% CI for the proportion of patients achieving partial response (PR) or better after 4 cycles of pembrolizumab therapy. The calculation will be performed using R clinfun package (www.r-project.org).

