6.8 Participant Replacement Strategy

If a participant is enrolled but does not receive any doses of pembrolizumab, the participant may be replaced.

If a participant is enrolled and receives less than 4 cycles of therapy and discontinues therapy or withdraws from the study for reasons other than disease progression, the participant will not be evaluated for the primary efficacy endpoint and will be replaced. However, all participants who receive at least one dose of pembrolizumab will be included in the safety analysis for adverse events (including those that received < 4 cycles of therapy).

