7.1 Evaluation of Efficacy: Antitumor Effect – Hematologic Tumors

Measurement of antitumor effect will be primarily through tumor markers (SPEP/SPIE, FLC, UPEP/UPIE, and bone marrow biopsy [where applicable]) as per International Myeloma Working Group (IMWG) Uniform Response Criteria. Only participants that complete at least 4 cycles of therapy or have progressive disease after at least one cycle of therapy will be included in the analysis for the primary endpoint. See Appendix 6 for additional details.

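### Progression during cycle 1 counts in the primary analysis under sections 3.2 and 6.8 but, read literally, not under 7.1, 9.1.1 and 9.3.1; the plan needs one rule, including whether such participants are replaced

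*Combined protocol and SAP*

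**What the plan says.** Two rules decide who enters the primary response analysis.

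- **Sections 3.2 and 6.8** work by exclusion. If someone has had fewer than four cycles and "discontinues therapy or withdraws from the study for reasons other than disease progression, the participant will not be evaluated for the primary efficacy endpoint"; that participant is replaced. A dosed participant who stops because of progression is not excluded, whenever the progression occurs.
- **Sections 7.1, 9.1.1 and 9.3.1** work by inclusion. Section 7.1 is the strictest: "Only participants that complete at least 4 cycles of therapy or have progressive disease after at least one cycle of therapy" enter the primary analysis. Section 9.1.1 bases the stage 1 response rate on patients who "have completed at least 4 cycles of therapy or have progressive disease after at least one cycle of therapy". Section 9.3.1 says that participants who "complete at least 4 cycles of therapy or have progressive disease after at least one cycle of therapy will be included in the analysis".

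Table 5.1 sets a cycle at 21 days, with one infusion on Day 1.

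On replacement, 6.8 covers only those who stop for reasons other than progression. Section 9.1.1 covers those who withdraw, or drop out because of toxicity, before meeting its conditions. Sections 5.3 and 9.2 define stage 1 by 15 evaluable participants.

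The decision rules in 9.1.1 are counts. At stage 1: "The trial will be terminated at Stage 1 if 0 or 1 response is observed; otherwise, it will continue to Stage 2". The null hypothesis is rejected with 6 or more responses in 25.

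**The concern.** Take a participant dosed on C1D1 who has a new plasmacytoma or myeloma-related hypercalcemia on day 15, both of which are progression criteria in 7.1.2. Sections 3.2 and 6.8 keep this participant, who cannot be a response. Under 7.1, 9.1.1 and 9.3.1 the same participant has neither completed four cycles nor, on a literal count of days, progressed after a cycle. No section reconciles the two rules, so the same data can give two denominators.

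The error can go only one way. Everyone affected is a non-responder, so leaving them out can only raise the response rate. The rate drives the stage 1 stop, the final test and the reported estimate. In a trial of 25, the choice of denominator should not be open once the data have been seen.

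**Working it through.** **Inputs.** From 9.1.1: null response rate 10%, target 30%, one-sided 5% error, 80% power; 15 participants in stage 1, stop at 0 or 1 response; 25 in total, reject at 6 or more; early stopping probability 55% under the null. From Table 5.1: a cycle of 21 days. Not in the documents, so assumed: the share *f* of dosed participants who progress in cycle 1.

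**Step 1: reproduce the plan's figures.**

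Early stopping at 10%: P(X ≤ 1 of 15) = 0.9^15 + 15 × 0.1 × 0.9^14 = 0.206 + 0.343 = 0.549.

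Rejection: P = Σ (x = 2 to 15) P(X1 = x) × P(X2 ≥ 6 − x), with X1 ~ Bin(15, p) and X2 ~ Bin(10, p). This gives 0.0328 at p = 0.10 and 0.8017 at p = 0.30. A search over two-stage designs returns the same minimax design. The stated 55%, 5% limit and 80% all hold.

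**Step 2: dropped and not replaced.** If 15 and then 10 more are dosed and cycle 1 progressors are merely left out, the number of responses is unchanged. The cut-offs are counts, so the false-positive rate stays at 3.3% and early stopping at 55%. Only the denominator shrinks. With 6 responses and 2 participants dropped, the crude rate reads 6/23 = 26.1% instead of 6/25 = 24.0%. The UMVUE, p-value and 95% CI planned in 9.3.1 would then be calculated for a set smaller than the 25 of the design.

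**Step 3: dropped and replaced.** The evaluable numbers stay at 15 and 25, but only non-responders are removed. A true rate of 10% among all dosed becomes 0.10/(1 − *f*) among the evaluable, which goes into the formulas of step 1.

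| Assumed *f* | Evaluable rate | False-positive rate | Early stopping |
|---|---|---|---|
| 0% | 10.0% | 3.3% | 54.9% |
| 4% | 10.4% | 3.9% | 52.7% |
| 8% | 10.9% | 4.7% | 50.4% |
| 12% | 11.4% | 5.6% | 47.9% |

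The false-positive rate reaches 5% at *f* of about 9.5% (evaluable rate 11.1%). At the rejection boundary with 2 removed and replaced, the reported crude rate is 6/25 = 24.0%, against 6/27 = 22.2% of those dosed.

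**Step 4: which of steps 2 and 3 applies.** The documents do not say. Section 6.8 does not list cycle 1 progressors for replacement. Section 9.1.1 does not name them, although 6.7 allows progression as a reason for withdrawal, which might bring them under its withdrawal wording. The call in 5.3 and 9.2 for 15 evaluable participants points toward making the number up.

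**The case against.** The strongest reply is that one cycle means one infusion given. Each cycle has a single infusion on Day 1, and the plan elsewhere treats cycles and treatments as the same count: 35 cycles in 3.1 become 35 treatments in 6.6. On that reading every dosed progressor has had a cycle and the five sections agree. This is tenable, but the text does not say it, and 7.2 refers to a dose when it means a dose.

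Second, the exclusion is not equally firm. Only 7.1 is worded as exclusive; 9.3.1 lists who is included, and the removal clause in 9.1.1 does not name progression. Likewise, 3.2 and 6.8 never use the term non-responder; that status is inferred. These points stand, and they show that the rule needs to be written down.

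Third, few participants may be affected. After C1D1 the next scheduled myeloma markers are at C5D1, and Appendix 6 requires two consecutive assessments for progression, so confirmation of a day 15 finding could fall after day 21. Cycle 1 progression would surface only through clinical findings, the calcium in the chemistry panels at C1D8 and C2D1, or unscheduled markers and imaging. This also stands, and it limits the likely size.

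A reader might go further and infer that the plan definitely removes its fastest failures, or that the type I error exceeds 5%. The documents support neither. The first depends on the literal reading of a cycle. The second needs replacement, which is unsettled, and more than about 9.5% of dosed participants progressing within 21 days, a rate that no section gives.

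**Conclusion.** The point holds as a conflict between definitions of the analysis set, with a bias of known direction and unknown size. The design figures themselves are correct. Without replacement, the harm is confined to the reported rate and to estimates that no longer match the design. With replacement, the false-positive rate at 10% rises from 3.3% to 3.9% or 4.7% for an assumed 4% or 8%, still within 5%, and to 5.6% for an assumed 12%. All three percentages of early progression are assumptions. The conflict disappears if one cycle was meant as one infusion; in that case the change below only makes the intention explicit.

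**What to change.** In 7.1, 9.1.1 and 9.3.1, replace the one-cycle condition for progressors with progression at any time after the first dose, which matches 3.2 and 6.8. Add one sentence stating that these participants are non-responders, count toward the 15 and the 25, and are not replaced. The planned properties then apply as calculated: 3.3% false-positive rate, 80% power, 55% early stopping. The change does not by itself cover death in cycle 1 without documented progression, so the added sentence should say how that is counted too.

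The cost is one phrase in three sections and one added sentence, with no change to treatment, visits or sample size. The observed response rate may be slightly lower.
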